### 3.6. Missing Data and Outliers

#### 3.6.1. Missing Data

In general, missing data will not be imputed unless imputation methods for handling missing data are specified.

For missing last dosing date of a study drug, imputation rules are described in Section 3.8.1. The handling of missing or incomplete dates for adverse event (AE) onset is described in Section 7.1.5.2 and for prior and concomitant medications in Section 7.5.

For analyses of categorical HCV RNA data, missing posttreatment HCV RNA data will have the missing data imputed. Missing on-treatment HCV RNA will have missing data imputed up to the date of the last dose (for on-treatment displays). If the study day associated with the last dosing date of any study drug is greater than or equal to the lower bound of a visit window, and the value at the visit is missing, then the value will be imputed. If the study day associated with the last dosing date is less than the lower bound of a visit window then the on-treatment value at that visit will remain missing.

If an HCV RNA data point is missing and is preceded and followed in time by values that are “< LLOQ target not detected (TND),” then the missing data point will be set to “< LLOQ TND.” If a data point is missing and preceded and followed by values that are “< LLOQ detected,” or preceded by “< LLOQ detected” and followed by “< LLOQ TND,” or preceded by “< LLOQ TND” and followed by “< LLOQ detected,” then the missing value will be set to “< LLOQ detected.” In these situations the data point will be termed a bracketed success; otherwise, the data point will be termed a bracketed failure (ie,  $\geq$  LLOQ detected). If a data point is missing and is not bracketed, the missing data point will also be termed a failure (ie,  $\geq$  LLOQ detected).

For the analyses of continuous HCV RNA efficacy data, when and only when a missing HCV RNA value is imputed as “< LLOQ TND” or “< LLOQ detected” according to the imputation rule described above, the corresponding continuous value will be imputed to LLOQ – 1 IU/mL (ie, HCV RNA 14 IU/mL). No other imputation will be performed for continuous HCV RNA data.

For the analyses of continuous HIV RNA data, for subjects with a missing HIV RNA value in a visit window that is bracketed by prior and subsequent values, the numerical value of HIV RNA will be imputed using the larger value. No other imputation will be performed for HIV RNA data.

Except for the imputation rules described above, values for other missing data (including all safety data) will not be imputed.

### **3.6.2. Outliers**

Outliers will be identified during the data management and data analysis process, but no sensitivity analyses will be conducted. All data will be included in the data analysis.

### **3.7. Data Handling Conventions and Transformations**

By-subject listings will be presented for all subjects in the Safety Analysis Set sorted by subject ID number, visit date, and time (if applicable) unless otherwise specified. Data collected on log forms, such as AEs, will be presented in chronological order within subject.

Age (in years) on the date of the first dose of study drug and sex at birth will be used for analyses and presentation in listings.

If a subject was not dosed with study drug at all, the date that the informed consent was signed will be used for age calculation as appropriate. For some countries, only birth year is collected on the eCRF. In those cases, “01 January” will be used for the unknown birth day and month for the purpose of age calculation, unless age is captured on the eCRF.

Non-PK data that are continuous in nature but are < LLOQ or above the upper limit of quantitation will be imputed as follows:

- A value that is 1 unit less than the limit of quantitation will be used for calculation of descriptive statistics if the datum is reported in the form of “< x” (where x is considered the limit of quantitation). For example, if the values are reported as < 50 and < 5.0, values of 49 and 4.9, respectively, will be used for calculation of summary statistics. An exception for this rule is any value reported as < 1. For the values reported as < 1 or < 0.1, values of 0.9 or 0.09, respectively, will be used for calculation of summary statistics.
- A value that is one unit above the limit of quantitation will be used for calculation of descriptive statistics if the datum is reported in the form of “> x” (where x is considered the limit of quantitation). Values with decimal points will follow the same logic as above.
- The limit of quantitation will be used for calculation of descriptive statistics if the datum is reported in the form of “≤ x” or “≥ x” (where x is considered the limit of quantitation).

The COBAS® AmpliPrep/COBAS® TaqMan® HCV Quantitative Test, version 2.0 will be used to determine HCV RNA results in this study. The LLOQ of the assay is 15 IU/mL.

When the calculated HCV RNA IU/mL is within the linear range of the assay, the result will be reported as the “<< numeric value>> IU/mL.” This result is referred to in this document as the numeric result or as “≥ LLOQ detected” for categorical results.

When HCV RNA is not detected, the result will be reported as “No HCV RNA detected” or “target not detected.” This result is referred to in this document as “< LLOQ target not detected” or “< LLOQ TND.”

When the HCV RNA IU/mL is less than the LLOQ of the assay, the result will be reported as “< 15 IU/mL HCV RNA detected.” This result is referred to in this document as “< LLOQ detected.”

The overall category of HCV RNA < LLOQ includes “< LLOQ TND” and “< LLOQ detected.”

For numerical HCV RNA data, values below the LLOQ will be set to LLOQ – 1 IU/mL. HCV RNA values returned as “target not detected” will also be set to LLOQ – 1 IU/mL.

HIV RNA in this study will be measured using the AmpliPrep/COBAS® TaqMan® HIV-1 Test, v2.0. The LLOQ of the assay is 20 copies/mL.

For the analyses of continuous HIV RNA data, for missing HIV RNA values in a visit window that are bracketed by prior and subsequent values, the numerical value of HIV RNA will be imputed using the larger value. Values returned as “< 20 copies/mL HIV-1 RNA detected” or “No HIV-1 RNA detected” will be set to the LLOQ minus 1 (ie, HIV RNA 19 copies/mL).

If methods based on the assumption that the data are normally distributed are not adequate, analyses may be performed on transformed data (eg, log10 scale), or nonparametric analysis methods may be used, as appropriate.

### **3.8. Analysis Visit Windows**

#### **3.8.1. Definition of Study Day**

Study day is the day relative to the date of the first dose of any study drug. Study Day 1 will be defined as the day of first dose of any study drug.

Study day will be calculated from the date of the first dose of study drug and derived as follows:

- For postdose study days: Assessment Date – First Dose Date + 1
- For days prior to the first dose: Assessment Date – First Dose Date

If there are subjects for whom the date of the last dose of study drug is unknown because the subject was lost to follow-up and not able to be contacted, the date of the last dose will be estimated using the maximum of nonmissing study drug start or stop dates, visit dates, and laboratory collection dates (posttreatment visits and unscheduled visits will not be included).

#### **3.8.2. Analysis Visit Windows**

Subject visits may not occur on protocol-specified days. Therefore, for the purpose of analysis, observations will be assigned to analysis windows.

In general, the baseline value will be the last nonmissing value on or prior to the date of the first dose of study drug.

HCV RNA, vital signs, safety laboratory data, HIV-1 RNA and CD4 counts (HIV-1 RNA and CD4 counts will be assessed for subjects with HIV coinfection only) collected up to the date of the last dose of study drug plus 3 days will be considered to be on-treatment data; HCV RNA, vital signs, safety laboratory data, and HIV-1 RNA and CD4 counts collected after the date of the last dose of study drug plus 3 days will be considered posttreatment data. The analysis windows for on-treatment HCV RNA, vital signs, safety laboratory data, and HIV-1 RNA and CD4 counts are provided in [Table 3-1](#).

**Table 3-1. Analysis Windows for On-treatment HCV RNA, Vital Signs, Safety Laboratory Data, HIV-1 RNA and CD4 Counts**

Nominal Visit	HCV RNA, Vital Signs, Safety Laboratory Data, HIV-1 RNA and CD4 Counts			Urinalysis, Coagulation Tests, CPT Score and Body Weight		
	Nominal Day	Lower Limit	Upper Limit	Nominal Day	Lower Limit	Upper Limit
Baseline	1	(none)	1	1	(none)	1
Week 2	14	2	21	NA	NA	NA
Week 4	28	22	42	NA	NA	NA
Week 8	56	43	70	NA	NA	NA
Week 12	84	71	≥ 85	84	2	≥ 85

HCV RNA, vital signs, safety laboratory data, and HIV-1 RNA and CD4 counts collected after the date of the last dose of study drug plus 3 days will be assigned to the posttreatment follow-up (FU) visit. Visit windows will be calculated from the date of the last dose (ie, FU Day = collection date – the last dose date) as shown in [Table 3-2](#).

**Table 3-2. Analysis Windows for Posttreatment HCV RNA, Vital Signs and Safety Laboratory Data, HIV-1 RNA and CD4 Counts**

Nominal FU a Visit	HCV RNA			Vital Signs, HIV-1 RNA, CD4 Counts and Other Safety Laboratory Data b		
	Nominal FU Day	Lower Limit	Upper Limit	Nominal FU Day	Lower Limit	Upper Limit
FU-4	28	21	69	28	4	30
FU-12	84	70	146	NA	NA	NA

a FU-x visit = posttreatment Week-x follow-up visit.

b Posttreatment vital signs, safety labs, HIV-1 RNA, and CD4 counts will be summarized only for the FU-4 visit (ie, up to 30 days after last dose).

### 3.8.3. Selection of Data in the Event of Multiple Records in an Analysis Window

Depending on the statistical analysis method, a single value may be required for each analysis window. For example, change from baseline by visit usually requires a single value, whereas a time-to-event analysis would not require 1 value for each analysis window.

If there are multiple valid nonmissing numeric observations in an analysis window, and a single value is needed, records will be chosen based on the following rules:

- For baseline, the last available record on or prior to the date of the first dose of study drug will be selected. If there are multiple records with the same time or no time recorded on the same day, the arithmetic mean will be used for the baseline value.
- For postbaseline visits:
  - The record closest to the nominal day for that visit will be selected, except for HCV RNA posttreatment FU visits, for which the latest record in the analysis window will be selected.
  - If there are 2 records that are equidistant from the nominal day, the later record will be selected.
  - If there is more than 1 record on the selected day, the arithmetic mean will be used, unless otherwise specified.
- If there are multiple valid nonmissing categorical observations in an analysis window, records will be selected as follows:
  - For baseline, the last available record on or prior to the date of the first dose of study drug will be selected. If there are multiple records with the same time or no time recorded on the same day, the value with the lowest severity will be selected (eg, normal will be selected over abnormal).
  - For postbaseline visits, the same rules described above for postbaseline numeric observations will be followed, except if there are multiple records on the same day, in which case the most conservative value will be selected (eg, abnormal will be selected over normal).

## 4. SUBJECT DISPOSITION

### 4.1. Subject Enrollment and Disposition

A summary of all enrolled subjects will be provided for each investigator by treatment group and overall. The summary will present the number and proportion of subjects in all enrolled subjects. For each column, the denominator for the percentage calculation will be the total number of subjects for that column.

A similar enrollment table will be provided by treatment group and overall by prior HCV treatment (treatment naive or treatment experienced). The denominator for the proportion of subjects in the stratum will be the total number of subjects in the Safety Analysis Set within that stratum. If there are discrepancies in the value used for stratification assignment between the IWRS and the clinical database, the value collected in the clinical database will be used for the summary. A listing of subjects with the IWRS randomization strata that differ from stratification factor data entered in the clinical database at the time of data finalization will be provided.

The randomization schedule used for the study will be provided as an appendix to the CSR.

A summary of subject disposition will be provided for each treatment group and overall for all screened subjects. The summary will present the number of subjects screened, the number of subjects not randomized, the number of subjects randomized, the number of subjects randomized but never treated, and the number of subjects in each of the categories listed below:

- Treated (Safety Analysis Set)
- In the FAS
- In the PK Analysis Set
- Completed study treatment
- Did not complete study treatment with reasons for premature discontinuation of study treatment
- Completed study
- Did not complete study with reasons for premature discontinuation of study

For the proportion of subjects who completed or did not complete study treatment or the study, the denominator for the percentage calculation will be the total number of subjects in the Safety Analysis Set. Among subjects who completed study treatment or discontinued study treatment, the number of subjects will be summarized for the following:

- No HCV posttreatment Week 4 assessment and thereafter (No HCV FU-4 and thereafter)
- With HCV posttreatment Week 4 assessment but no HCV posttreatment Week 12 and thereafter (With HCV FU-4 but No FU-12 and thereafter)

If a subject did not have any HCV RNA assessment  $\geq 21$  days after the last dose of study drug (ie, lower bound of FU-4 visit for HCV RNA data), the subject will be categorized as having “No HCV FU-4 and thereafter.” If a subject had the HCV FU-4 assessment but did not have any HCV RNA assessment  $\geq 70$  days after the last dose of any study drug (ie, lower bound of FU-12 visit for HCV RNA data), the subject will be categorized as having “With HCV FU-4 but No FU-12 and thereafter.”

The total number of subjects who were randomized and the number of subjects in each of the disposition categories listed above will be depicted by a flowchart.

A summary of reasons for screen failure will also be provided.

The following by-subject listings will be provided by subject ID number in ascending order to support the above summary tables:

- Disposition for subjects who complete study treatment and study
- Disposition for subjects who did not complete study treatment and/or study with reasons for premature discontinuation of study treatment and/or study
- Lot number and kit ID (if applicable)

#### **4.2. Extent of Exposure and Adherence**

The extent of exposure to study drug will be examined by assessing the total duration of study drug exposure and the level of adherence to the study regimen/drug specified in the protocol for subjects in Safety Analysis Set.

##### **4.2.1. Duration of Exposure to Study Drug**

Total duration of exposure to the study regimen is defined as the date of the last dose of study regimen – the date of the first dose of study regimen + 1, regardless of any temporary interruptions in study drug dosing, and will be expressed in weeks using up to 1 decimal place (eg, 4.5 weeks). The date of first/last dose of study regimen is defined as the date of first/last dosing of SOF/VEL for subjects who were assigned to SOF/VEL treatment group, and the date of the earliest/latest dosing of SOF/VEL or RBV for subjects who were assigned to SOF/VEL+RBV treatment group.

The total duration of exposure to individual study drug is defined as the date of the last dose of study drug (either SOF/VEL or RBV) – the date of the first dose of study drug (either SOF/VEL or RBV) + 1, regardless of any temporary interruptions in study drug administration, and will be expressed in weeks using up to 1 decimal place.

The total duration of exposure to the study regimen and to each individual study drug will be summarized using descriptive statistics (n, mean, SD, median, Q1, Q3, minimum, and maximum) and the number (ie, cumulative counts). The proportion of subjects exposed to the

study regimen through the following time periods: baseline /Day 1, Week 2 (Day 14), Week 4 (Day 28), Week 8 (Day 56), and Week 12 (Day 84) will also be presented. A 3-day window was applied to the last planned on-treatment visit to match the protocol-specified visit window. Summaries will be provided by treatment group and overall for the Safety Analysis Set.

#### 4.2.2. Adherence to Study Drug

The presumed total number of tablets administered to a subject will be determined by the data collected on the drug accountability eCRF using the following formula:

$$\text{Total Number of Doses Administered} = \left( \sum \text{No. of Tablets Dispensed} \right) - \left( \sum \text{No. of Tablets Returned} \right)$$

The level of adherence to study drug will be assessed based on the total amount of study drug administered relative to the total amount of study drug prescribed at baseline.

The level of adherence will be expressed as a percentage using the following formula:

$$\text{Level of Adherence}(\%) = \left( \frac{\text{Total Amount of Study Drug Administered}}{\text{Total Amount of Study Drug Prescribed at Baseline}} \right) \times 100$$

Note: If calculated adherence is greater than 100%, the result will be set to 100%.

In this study, the total amount of SOF/VEL (400/100 mg) prescribed for 12 weeks would require 84 SOF/VEL (400/100 mg) tablets. For Group 2 subjects, the prescribed weight-based RBV (200 mg tablet) would require 420 tablets (5 tablets/day × 84 days for subjects with baseline weight < 75 kg) or 504 tablets (6 tablets/day × 84 days for subjects with baseline weight ≥ 75 kg) for the 12 week treatment period.

Subjects who prematurely discontinue study drug due to lack of efficacy (ie, virologic failure) will have the total amount of study drug prescribed calculated up to the first date when virologic failure criteria were met. For virologic failure confirmed by 2 consecutive measurements, the date of the first measurement will be used. Study drug bottles that were dispensed on or after the subject first met virologic failure criteria will not be included in the calculation of adherence. If a bottle was dispensed and the bottle was returned empty, the number of tablets returned will be entered as zero. If a bottle was dispensed but not returned (missing), the number of tablets taken from that bottle will be counted as zero.

Descriptive statistics for the level of adherence (n, mean, SD, median, Q1, Q3, minimum, and maximum) with the number and proportion of subjects belonging to adherence categories (e.g., < 80%, ≥ 80 to < 90%, ≥ 90%) will be provided by treatment group for the Safety Analysis Set. No inferential statistics will be provided.

A separate by-subject listing of study drug administration and drug accountability will be provided by subject ID number (in ascending order) and visit (in chronological order).

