Nine subjects discontinued all study drugs due to an AE (SOF/VEL 12 Week group: 1.1%, 1 subject; SOF/VEL +RBV 12 Week group: 4.6%, 4 subjects; SOF/VEL 24 Week group: 4.4%, 4 subjects). No AE leading to discontinuation of study drugs was reported in > 1 subject. A total of 31.0% (27 of 87) of subjects had modified or interrupted RBV dosing due to AEs, and 10.3% (9 of 87) of subjects permanently discontinued RBV due to AEs while continuing SOF/VEL.

The majority of subjects had at least 1 Grade 3 or 4 laboratory abnormality (42.7% and 12.4%, respectively) with the highest rates observed in the SOF/VEL +RBV group (Grade 3: 43.7%; Grade 4 18.4%) due to a higher rate of hematologic abnormalities. The most commonly observed Grade 3 or 4 hematology laboratory abnormalities were decreased lymphocytes, hemoglobin, and platelet counts, all of which are a known effect of RBV therapy or expected in a subject population with decompensated liver disease.

The most commonly observed Grade 3 or 4 chemistry laboratory abnormalities were increased glucose and increased total bilirubin. All of the Grade 3 or 4 increased glucose abnormalities occurred in subjects with a history of diabetes mellitus or had elevated glucose at baseline or continuing through the posttreatment period. The majority of subjects with Grade 3 or 4 increased total bilirubin (71.7%, 22 of 31 subjects) were in the SOF/VEL +RBV 12 Week group, primarily in a pattern that was consistent with RBV-induced hemolysis.

No notable changes in vital signs (systolic blood pressure, diastolic blood pressure, and pulse) were reported during the study. No trends in electrocardiogram findings suggestive of cardiotoxicity were observed.

Conclusions

The conclusions from this interim analysis were as follows:

- Treatment with SOF/VEL ±RBV for 12 or 24 weeks in subjects with decompensated cirrhosis resulted in high SVR12 rates:
 - In the SOF/VEL 12 Week group, the SVR12 rate was 83.3% (75 of 90 subjects).
 - In the SOF/VEL +RBV 12 Week group, the SVR12 rate was 94.3% (82 of 87 subjects).
 - In the SOF/VEL 24 Week group, the SVR12 rate was 87.8% (79 of 90 subjects).

- The SVR12 rates were highest in subjects treated with SOF/VEL +RBV for 12 weeks with few virologic failures:
 - In subjects with genotype 1 HCV infection, the virologic failure rate was 1.5% (1 of 68 subjects).

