7.3. Group 2: Subjects administered SOF/VEL+ RBV

Dose modification for subjects administered SOF/VEL+RBV should be performed according to the prescribing information.

Dose reduction of SOF/VEL is not permitted.

Table 7-1. Ribavirin Dose Modification Guideline for Coadministration with SOVALDI

Laboratory Values	Reduce Ribavirin Dose to 600 mg/day ^a If:	Discontinue Ribavirin If: ^b
Hemoglobin in patients with no cardiac disease	<10 g/dL	<8.5 g/dL
Hemoglobin in patients with history of stable cardiac disease	≥2 g/dL decrease in hemoglobin during any 4 week treatment period	<12 g/dL despite 4 weeks at reduced dose

a The daily dose of ribavirin is administered orally in two divided doses with food.

b Once ribavirin has been withheld due to either a laboratory abnormality or clinical manifestation, an attempt may be made to restart ribavirin at 600 mg daily and further increase the dose to 800 mg daily. However, it is not recommended that ribavirin be increased to the original assigned dose (1000 mg to 1200 mg daily).

If RBV is permanently discontinued, SOF should also be discontinued.

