### **3.4. Examination of Subject Subsets**

The following subject subsets will be explored for the primary efficacy endpoint:

- Age (< 65 years, ≥ 65 years)
- Sex (male, female)
- Race (White, Asian)
- Ethnicity (Hispanic or Latino, Not Hispanic or Latino)
- Baseline body mass index (BMI) (< 30 kg/m^2, ≥ 30 kg/m^2)
- IL28B genotype (CC, non-CC; with non-CC further broken down to CT, TT)
- Baseline HCV RNA (< 800,000 IU/mL, ≥ 800,000 IU/mL)
- Baseline alanine aminotransferase (ALT; ≤ 1.5 × upper limit of normal [ULN], > 1.5 × ULN)
- Prior HCV treatment experience (treatment naive, treatment experienced)
- HIV coinfection (yes, no, missing)
- Prior HCV treatment response (nonresponder, relapse/breakthrough, other) for treatment-experienced subjects

- Completed study treatment, discontinued study treatment
- Adherence to study regimen ( $< 80\%$ ,  $\geq 80\%$ )
- Adherence to SOF/VEL ( $< 80\%$ ,  $\geq 80\%$ )

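### Ribavirin adherence is divided by the baseline prescription, so a fully compliant Group 2 subject can score under 80% if the protocol-directed reduction to 600 mg/day comes before about Week 6 or Week 7

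*SAP*

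**What the plan says.** SAP 4.2.2 takes tablets dispensed minus tablets returned as the amount taken. It expresses this as a percentage "relative to the total amount of study drug prescribed at baseline", capped at 100%. For SOF/VEL, the amount "prescribed for 12 weeks would require 84 SOF/VEL (400/100 mg) tablets". The RBV denominator depends on body weight. The lighter group is set at 420, derived as "5 tablets/day × 84 days for subjects with baseline weight < 75 kg"; everyone else in Group 2 is set at 504, from six a day over the same period. The section shortens the denominator in one case only, stopping for virologic failure. For a bottle that never comes back, "the number of tablets taken from that bottle will be counted as zero".

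The results are summarized by treatment group (Table 15.8.4) in bands such as below 80%, 80% to below 90%, and 90% or more, without inferential statistics. SAP 3.4 uses the 80% cut for two SVR12 subgroups: "Adherence to study regimen", and adherence to SOF/VEL alone. The SAP does not say how SOF/VEL and RBV are combined into regimen adherence.

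Protocol 7.3, Table 7-1, carries the instruction "Reduce Ribavirin Dose to 600 mg/day" at listed hemoglobin values. Protocol 5.4.4 leaves further dose modification to the investigator. Protocol 7.2 and 7.3 allow no dose reduction of SOF/VEL.

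**The concern.** SAP 4.2 sets out to measure adherence to the regimen that the protocol specifies. A subject who takes 600 mg/day because Table 7-1 says so is following the protocol, yet the formula counts every tablet withdrawn by the reduction as a missed tablet. What it then measures is the percentage of the planned dose received. That is a useful exposure measure, but it is not adherence. The adjustment for virologic failure shows that the SAP already accepts, in one setting, that tablets no longer prescribed should not count against the subject.

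The situation is foreseeable. Subjects may enter with hemoglobin as low as 10 g/dL (Protocol 4.3), which is where the Table 7-1 threshold lies for subjects without cardiac disease.

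At stake is how a reader interprets the low-adherence group in the RBV arm. It can mix subjects who missed doses with subjects who obeyed a reduction. The unreturned-bottle rule is a second, separate route by which a compliant subject in either arm can land in that group.

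**Working it through.** **Inputs.** RBV tablets are 200 mg (Protocol 5.4.1). The baseline dose is 5 tablets/day below 75 kg and 6 tablets/day at 75 kg or more (Protocol 5.4.4). The reduced dose is 600/200 = 3 tablets/day (Table 7-1). Treatment lasts 84 days. Bottles hold 28 SOF/VEL tablets (Protocol 5.2.2) or 168 RBV tablets (Protocol 5.4.2).

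**The plan's own figures.** 1 × 84 = 84, 5 × 84 = 420 and 6 × 84 = 504. All three reproduce.

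**Directed reduction.** The documents do not fix when a reduction occurs. Assume one reduction to 3 tablets/day after d full-dose days, no later change, and every prescribed tablet taken.

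- Baseline 1000 mg: [5d + 3(84 − d)]/420 = (252 + 2d)/420.
- Baseline 1200 mg: [6d + 3(84 − d)]/504 = (252 + 3d)/504.

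| Full-dose days d | 1000 mg | 1200 mg |
|---|---|---|
| 0 | 252/420 = 60.0% | 252/504 = 50.0% |
| 14 (Week 2) | 280/420 = 66.7% | 294/504 = 58.3% |
| 28 (Week 4) | 308/420 = 73.3% | 336/504 = 66.7% |
| 42 (Week 6) | 336/420 = 80.0% | 378/504 = 75.0% |
| 56 (Week 8) | 364/420 = 86.7% | 420/504 = 83.3% |

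The 80% boundary follows directly:

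- 1000 mg: 252 + 2d < 0.80 × 420 = 336 gives d < 42, so at most 41 full-dose days.
- 1200 mg: 252 + 3d < 0.80 × 504 = 403.2 gives d < 50.4, so at most 50 full-dose days. At d = 50 the score is 402/504 = 79.8%; at d = 51 it is 405/504 = 80.4%.

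With the amount prescribed at the time as denominator, the same subjects score 100%: 280/280 or 294/294 at Week 2, 308/308 or 336/336 at Week 4, and 364/364 or 420/420 at Week 8.

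**Unreturned bottle.** If a compliant subject had used the whole bottle:

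- SOF/VEL: (84 − 28)/84 = 56/84 = 66.7%.
- RBV: (420 − 168)/420 = 252/420 = 60.0%, or (504 − 168)/504 = 336/504 = 66.7%.

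The score falls below 80% only if the missing bottle had supplied at least 17 of the 84 SOF/VEL tablets (67/84 = 79.8%), 85 of the 420 RBV tablets (335/420 = 79.8%) or 101 of the 504 RBV tablets (403/504 = 79.96%). If a subject under 75 kg uses RBV bottles in sequence, the third supplies 420 − 2 × 168 = 84 tablets. Losing it gives 336/420 = 80.0%, which is not below the cut.

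**How often.** The documents give no direct figure. In ASTRAL-4, 31.0% (27 of 87) "of subjects had modified or interrupted RBV dosing due to AEs", but those subjects had CPT class B cirrhosis. In ASTRAL-2, 9.8% of the 12-week SOF+RBV arm had an AE leading to modification or interruption of any study drug, but only 14.3% of that trial's subjects had cirrhosis. If the share here lies between these values, about 10 to 31 of 100 Group 2 subjects would have a modification. The number misclassified would be some unknown part of that, because both figures cover changes of any kind at any time.

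**The case against.** The strongest reply is that the SAP states its convention openly, and that nothing inferential rests on it. SAP 4.2.2 rules out inferential statistics for adherence, and the primary analysis (SAP 6.1.2) is SVR12 with exact intervals in the FAS, without any adherence variable. The plan also gives the reader means to separate the two kinds of subject: SVR12 by Dose Modifications (Table 15.9.4.3), AEs leading to modification or interruption of RBV (Table 15.11.5.7), and by-subject listings of drug administration and accountability. Counting an unreturned bottle as zero is a prespecified, conservative convention. It is also the correct value if the bottle was unused, which can happen because Protocol 5.7 dispenses a spare SOF/VEL bottle on Day 1.

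Most of this stands, and it is why the point is minor. It does not remove the point. Table 15.9.4.3 helps interpretation but reclassifies nobody, and Table 15.8.4 would still label as poorly adherent some subjects who took everything prescribed.

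A reader might infer more than the documents support:

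- *Every compliant subject with a directed reduction is classed under 80%.* No. A Week 8 reduction leaves the score above 80% at either baseline dose.
- *The SVR12-by-adherence result is therefore wrong.* Not shown. SAP 3.4 lists no subgroup for RBV adherence alone, and the reach into the regimen subgroup depends on the missing combination rule.
- *The whole problem falls on the RBV arm.* Only the dose-reduction part does. The bottle rule covers both drugs and both arms.

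**Conclusion.** The concern holds with its timing condition attached. The fixed denominator can put a fully compliant Group 2 subject under 80% for RBV if the reduction to 600 mg/day follows at most 41 full-dose days (1000 mg at baseline) or 50 (1200 mg). This assumes a single reduction with no later change and complete intake. A Week 8 reduction still costs the subject the top adherence band, but not the 80% class.

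The RBV part of Table 15.8.4 is distorted in Group 2 only. The regimen-adherence subgroup for SVR12 may be affected. RBV reductions do not touch the SOF/VEL adherence subgroup, and the primary SVR12 analysis is unaffected by either rule. The unreturned-bottle rule is a separate effect: it applies in both arms, can reach the SOF/VEL measure, and matters only when the missing bottle was largely used. The number of subjects affected cannot be estimated from the documents. Severity is minor, and no view is taken on the RBV dosing rule itself.

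**What to change.** Amend SAP 4.2.2 and, where needed, SAP 3.4:

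1. Define adherence as tablets taken divided by tablets prescribed at the time. Update the RBV denominator from recorded, investigator-directed dose changes, so that a subject's own omissions still count as missed.
2. Report the percentage of the planned baseline dose separately and label it as exposure. This keeps the quantity that the present formula produces.
3. State how SOF/VEL and RBV are combined into regimen adherence for the SVR12 subgroup.
4. Flag subjects with an unreturned bottle, and show their adherence category with that bottle counted as zero and as fully taken.

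The cost is SAP wording, a little programming and one extra exposure row. No new data are needed: Protocol 10.1.5 requires study drug dates with dose regimen in the source records, listing 16.2.5.1 presents drug administration, and Table 15.9.4.3 already needs dose-modification data. No dosing rule changes.
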